2.8.2 Laboratory data

On analyzing laboratory, data from all sources (central and local laboratories) will be combined. The summaries will include all assessments available for the lab parameter collected no later than 30 days after the last study treatment administration.

The following summaries will be produced for hematology and biochemistry laboratory data (by laboratory parameter and treatment):

- Shift tables using CTC grades to compare baseline to the worst on-treatment value
- For laboratory tests where CTC grades are not defined, shift tables using the low/normal/high/(low and high) classification to compare baseline to the worst on-treatment value.

The following listings will be produced for the laboratory data:

- Listing of all CTC grade 3 or 4 laboratory toxicities

Table 2-4 lists those entire laboratory parameters for which CTCAE grades are defined, Table 2-5 lists the remaining laboratory parameters for which shift tables were based upon the local lab normal range.

Table 2-4 Laboratory parameters to be presented in grade shift tables based on CTC grade

Hematology	Biochemistry	Coagulation
White blood cell count (WBC)	AST (SGOT)	Fibrinogen
Hemoglobin	ALT (SGPT)	PT
Platelets counts	Total Bilirubin	PTINR
Abs. Neutrophils	Albumin	PTT
Abs. Lymphocytes	Creatinine	
	Alkaline Phosphatase	
	Glucose	
	Calcium	
	Sodium	
	Magnesium	
	Potassium	
	Hypophosphatemia	

ALT (SGPT) = Alanine aminotransferase/glutamic pyruvic transaminase; AST (SGOT) = Aspartate aminotransferase/glutamic oxaloacetic transaminase; PT = prothrombin time; PTINR = prothrombin time International normalized ratio

Table 2-5 Laboratory parameters to be presented in shift tables based on local lab normal ranges

Hematology	Biochemistry	Coagulation
Absolute eosinophils	BUN	
Absolute basophils	Total protein	
Absolute monocytes	Direct bilirubin	
Red blood cell count (RBC)	LDH	
Hematocrit (HCRIT)		

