10.5.3.3 Laboratory abnormalities

For laboratory tests covered by the CTCAE version 4.03 laboratory data will be graded accordingly. For laboratory tests covered by CTCAE, a grade 0 will be assigned for all non-missing values not graded as 1 or higher. Grade 5 will not be used.

For laboratory tests where grades are not defined by CTCAE, results will be graded by the low/normal/high classifications based on laboratory normal ranges, or alternative clinically meaningful limits.

The following by-treatment summaries will be generated separately for hematology, biochemistry and urinary laboratory tests:

- frequency table for newly occurring on-treatment grades 3 or 4
- shift tables using CTCAE grades to compare baseline to the worst on-treatment value
- for laboratory tests where CTCAE grades are not defined, shift tables using the low/normal/high/(low and high) classification to compare baseline to the worst on-treatment value.
- listing of all laboratory data with values flagged to show the corresponding CTCAE grades and the classifications relative to the laboratory normal ranges.

In addition to the above mentioned tables and listings, other exploratory analyses, for example figures plotting time course of raw or change in laboratory tests over time or box plots may be specified in the RAP.

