2.8 Safety analyses

A secondary objective of the study is to characterize the safety and tolerability of BGJ398.

The assessment of safety is based on the frequency and severity of AEs and SAEs, changes in hematology and chemistry values, specifically those associated with calcium/phosphate homeostasis and renal function, and on the number of laboratory values that fall outside of pre-determined ranges (CTCAE v 4.03 grading limits or normal ranges as appropriate). Other safety (e.g., ECGs, vital signs and special tests, e.g. pregnancy test) analyses will be considered as appropriate.

All safety analyses will be based on the safety set.

The safety summary tables will include only on-treatment assessments. All safety assessments will be listed, and those collected later than 30 days after study treatment discontinuation will be flagged.

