2.11 Interim analysis

Not applicable.

3 Sample size calculation

The operating characteristics of the design have been assessed via simulations (see Table 3-1 below). For each scenario, 1000 trials were simulated. A scenario was defined by assumption regarding the true PFS6 rate, an accrual rate of one patient per month with the final analysis taking place after the last patient completed 6 cycles of treatment or discontinued. A success was defined as follows:

Prob (PFS6 > 25%) > 80% and Prob (PFS6 > 40%) > 50% at the final analysis.

Table 3-1 Operating characteristics of study design

	True PFS6					
	0.16	0.25	0.35	0.4	0.45	0.5
Prob. of stopping at interim	0.870	0.506	0.165	0.082	0.035	0.014
Average sample size	21.589	27.016	31.799	32.922	33.547	33.822
Prob. of success (final)	0.000	0.003	0.227	0.488	0.746	0.917
Average study duration (months)	20.674	27.388	33.650	35.269	36.261	36.807

Assuming a true PFS6 rate of 50% and a uniform accrual of one patient per month, with 34 patients in total (~27 PFS events), there is about 92% chance to achieve success at the end of the study.

4 Change to protocol specified analyses

Interim analysis is planned in the CSP: an interim analysis for futility was planned to be carried out once 10 patients in the PPS have completed 6 cycles of treatment or discontinued earlier. No actual interim analysis was performed.

5 Appendix

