5.3 Laboratory parameters derivations

Grade categorization of lab values will be assigned programmatically as per NCI Common Terminology Criteria for Adverse Events (CTCAE) version 4.03. The calculation of CTCAE grades will be based on the observed laboratory values only, clinical assessments will not be taken into account. The criteria to assign CTCAE grades are given in Novartis internal criteria for CTCAE grading of laboratory parameters. The latest available version of the document based on the underlying CTCAE version 4.03 at the time of analysis will be used. For laboratory tests where grades are not defined by CTCAE v4.03, results will be graded by the low/normal/high (or other project-specific ranges, if more suitable) classifications based on laboratory normal ranges.

A severity grade of 0 will be assigned for all non-missing lab values not graded as 1 or higher. Grade 5 will not be used. For laboratory tests that are graded for both low and high values, summaries will be done separately and labelled by direction, e.g., sodium will be summarized as hyponatremia and hypernatremia.

Imputation Rules

CTC grading for blood differentials is based on absolute values. However, this data may not be reported as absolute counts but rather as percentage of WBC.

If laboratory values are provided as '<X' (i.e. below limit of detection) or '>X', prior to conversion of laboratory values to SI unit, these numeric values are set to X.

The following rules will be applied to derive the WBC differential counts when only percentages are available for a xxx differential

$$\text{xxx count} = (\text{WBC count}) * (\text{xxx \%value} / 100)$$

Further derivation of laboratory parameters might be required for CTCAE grading. For instance, corrected calcium can be derived using the reported total calcium value and albumin at the same assessment using the following formula:

$$\text{Corrected Calcium (mg/dL)} = \text{Calcium (mg/dL)} - 0.8 [\text{Albumin (g/dL)} - 4]$$

In order to apply the above formula, albumin values in g/L will be converted to g/dL by multiplying by 0.1), calcium values in mmol/L will be converted to mg/dL by dividing by 0.2495. For calculation of laboratory CTC grades 0 and 1, the normal range for derived corrected calcium is set to the same limits (in mg/dL) as for calcium.

CTC grades for the derived absolute WBC differential counts (neutrophils, lymphocytes) and corrected calcium will be assigned as described above for grading

6 Reference

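### The SAP's laboratory shift tables list phosphate only in the low direction and omit amylase and lipase, against the SAP's own rule

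*SAP*

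**What the plan says.** **The rule.** SAP 2.8.2 splits hematology and biochemistry tests in two. Those with CTC grades get a grade shift from baseline to the worst on-treatment value. The others get a shift by normal-range category. Table 2-4 is described as holding the graded tests. For the rest, "Table 2-5 lists the remaining laboratory parameters for which shift tables were based upon the local lab normal range". SAP 5.3 repeats the fallback ("For laboratory tests where grades are not defined by CTCAE v4.03, results will be graded by the low/normal/high") and adds that tests graded in both directions are summarized separately for low and high. Protocol 10.5.3.3 has the same rule: "for laboratory tests where CTCAE grades are not defined, shift tables using the low/normal/high/(low and high) classification".

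**The rows.** Phosphate appears once across both tables, as "Hypophosphatemia" in the biochemistry column of Table 2-4. Amylase and lipase do not appear.

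**The stated focus.** SAP 2.8 bases the safety assessment partly on changes in hematology and chemistry values, "specifically those associated with calcium/phosphate homeostasis and renal function". SAP Table 1-1 includes evaluation of laboratory values in the secondary tolerability endpoint.

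**Grades 3 and 4.** Protocol 10.5.3.3 calls for a "frequency table for newly occurring on-treatment grades 3 or 4". The corresponding output in SAP 2.8.2 is a "Listing of all CTC grade 3 or 4 laboratory toxicities". SAP section 4, which records departures from the protocol's analyses, mentions only the interim analysis ("No actual interim analysis was performed").

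**The concern.** The rule is sound, and the two lists read as its complete implementation: graded tests in one, everything else in the other. If the tables are programmed from them, phosphate is tabulated only in the direction opposite to the expected drug effect. Protocol 1.2.1.2.1 describes phosphate elevation as a marker of on-target FGFR inhibition, seen in most patients at 100 mg daily and above.

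The lists would also give no shift for amylase or lipase. The Amendment 2 rationale says that mild to moderate asymptomatic lipase increases have been seen with BGJ398, and that the related discontinuation criteria were relaxed. A reader of the study report would want a baseline-to-worst display for that test.

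Exclusion criterion 18 keeps out patients whose phosphorus is above the upper normal limit at entry. The missing phosphate table would therefore read mainly as a count of new high values, including rises never recorded as adverse events.

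**Working it through.** The plan gives no figure to reproduce here. The check is a comparison of lists, plus one illustration of scale.

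**Step 1. Inputs.**
- Protocol Table 7-3, biochemistry, 19 distinct tests: albumin, alkaline phosphatase, ALT, AST, calcium, chloride, creatinine, BUN/urea, potassium, sodium, magnesium, inorganic phosphorus, direct, indirect and total bilirubin, total protein, uric acid, amylase, lipase.
- SAP Table 2-4: 5 hematology + 12 biochemistry + 4 coagulation = 21 rows.
- SAP Table 2-5: 5 hematology + 4 biochemistry = 9 rows.

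**Step 2. Collected biochemistry tests against SAP rows.**

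| Status in SAP Tables 2-4 and 2-5 | Tests | Count |
|---|---|---|
| Row without restriction of direction | AST, ALT, total bilirubin, albumin, creatinine, alkaline phosphatase, calcium, sodium, magnesium, potassium (2-4); BUN, total protein, direct bilirubin (2-5) | 13 |
| Low direction only | phosphorus (2-4) | 1 |
| No row in either table | amylase, lipase, chloride, uric acid, indirect bilirubin | 5 |

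13 + 1 + 5 = 19.

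**Step 3. SAP rows against the Table 7-3 blood panels.** Glucose, LDH, fibrinogen and red blood cell count have SAP rows but are not in those panels. With mismatches both ways, the lists do not appear to have been reconciled with the protocol panel.

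**Step 4. Does the phosphate gap depend on how CTCAE v4.03 treats high phosphate?** The documents do not say whether it is graded, but the answer is the same either way.
- If it is graded, SAP 5.3 requires a separate high-direction summary, and Table 2-4 has none.
- If it is not graded, the low/normal/high rule applies, and Table 2-5 has no phosphate row.

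**Step 5. Amylase and lipase.** Protocol Table 6-3 gives limits for both: grade 3 above 2.0 to 5.0 times ULN, grade 4 above 5.0 times ULN. By the SAP's description they belong in Table 2-4. They are in neither table.

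**Step 6. Scale (illustration only).** Protocol 1.2.1.2.1 reports elevated phosphorus in 17 of 25 patients on the three-weeks-on, one-week-off schedule: 17/25 = 0.68. Assume that rate carries over to the 34 planned patients: 0.68 × 34 = 23.1, about 23 patients. A beta-binomial prediction for 34 new patients allows for uncertainty in the rate and for sampling variation:
- uniform prior, Beta(1 + 17, 1 + 8) = Beta(18, 9): mean 34 × 18/27 = 22.7; 95% prediction interval 14 to 30 (exact coverage 0.968);
- Jeffreys prior, Beta(17.5, 8.5): mean 34 × 17.5/26 = 22.9; interval 14 to 30 (exact coverage 0.966).

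This counts patients expected to have the finding. It does not count patients whose data would be lost, since many would also appear in AE tables.

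**The case against.** **The outputs may exist elsewhere.** The TFL shells define the actual tables and were not available. The public SAP also runs from 2.8.4.2 to 2.11 and has a blacked-out entry in its list of tables, so a phosphate summary could sit in removed text. This stands as a limit: one cannot conclude that raised phosphate has no planned summary anywhere. It does not rescue 2.8.2, whose text and tables are intact and whose lists do not match the rule beside them.

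**The rule may work per test.** On that reading, phosphate has a graded row and needs no second one. The wording of the fallback allows this, but the expected direction would still have no shift table, against the focus stated in SAP 2.8. The reading does nothing for amylase and lipase.

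**Adverse-event reporting covers much of this.** Protocol 8.1.2.1 makes a laboratory abnormality an adverse event when the protocol requires a dose hold or medication for it. Table 6-3 requires holds for grade 3 and 4 amylase or lipase and at the higher phosphate thresholds. Dose-change summaries, the grade 3/4 listing, full listings and the out-of-range counts mentioned in SAP 2.8 also remain. This is substantial cover. What is lost is rises that need no action, and the baseline-to-worst display itself.

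**Some items are minor.** Indirect bilirubin is total minus direct, and both of those have rows. The documents give chloride and uric acid no particular safety role. The four extra rows do no harm. For tests that have a grade shift table, the missing frequency table loses little information, though its removal is still undeclared. These points are fair, and those items are housekeeping.

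**Conclusion.** The concern holds, with high confidence, for the rows named in the SAP. The main defects are the missing high direction for phosphate and the absence of amylase and lipase. In all, 5 of 19 collected biochemistry tests have no row and 1 more has the low direction only.

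This should be corrected, but it does not threaten the trial's conclusions: no decision rule uses these tables, and the underlying values are listed. The practical harm depends on the outputs being programmed from these lists. The figure of about 23 of 34 patients (14 to 30) rests on the earlier rate carrying over to this population and only shows how common the untabulated finding could be.

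**What to change.** 1. Add inorganic phosphorus to Table 2-5 with a low/normal/high shift. Keep the Table 2-4 row, labelled as the low direction. The new row shows high values whether or not CTCAE v4.03 grades them.
2. Add amylase and lipase to Table 2-4.
3. Reconcile both tables with all of protocol Table 7-3. Place chloride, uric acid and indirect bilirubin in the table that fits their grading. Check glucose, LDH, fibrinogen and red blood cell count against the eCRF before changing those rows; do not simply delete them.
4. Either add the protocol's frequency table of newly occurring grades 3 or 4 to SAP 2.8.2, or record its removal in SAP section 4.
5. Make the TFL shells match.

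The cost is six added rows, one line in SAP 2.8.2 or section 4, and a check of the shells. Table 7-3 already collects the data for the added rows. No dose or clinical rule is affected.

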2.8.3 ECOG performance status

Frequencies and percentages for the categories of the ECOG performance scale will be listed.

Table 2-6 ECOG performance status

Grade	ECOG Status
0	Fully active, able to carry on all pre-disease performance without restriction
1	Restricted in physically strenuous activity but ambulatory and able to carry out work of a light or sedentary nature (e.g., light house work, office work)
2	Ambulatory and capable of all self-care but unable to carry out any work activities. Up and about more than 50% of waking hours
3	Capable of only limited self-care, confined to bed or chair more than 50% of waking hours
4	Completely disabled. Cannot carry on any self-care. Totally confined to bed or chair

Note: Grade 5 (dead) was removed from this table. This information will be collected on a separate (e)CRF page.

2.8.4 Other safety data**2.8.4.1 ECG and cardiac imaging data**

12-lead ECGs including PR, QRS, QT, and QTcF, will be obtained central/local for each subject during the study. ECG data will be read and interpreted centrally locally

The number and percentage of subjects with notable ECG values will be presented.

- QT, or QTcF
 - New value of > 450 and ≤ 480 ms
 - New value of > 480 and ≤ 500 ms
 - New value of > 500 ms
 - Increase from Baseline of > 30 ms to ≤ 60 ms
 - Increase from Baseline of > 60 ms
- HR
 - Increase from baseline $>25\%$ and to a value > 100 bpm

- Decrease from baseline >25% and to a value < 50 bpm
- PR
 - Increase from baseline >25% and to a value > 200 ms
 - New value of > 200 ms
- QRS
 - Increase from baseline >25% and to a value > 120 ms
- New values of QRS > 120 ms

A listing of notable ECG values will be produced. In the listing, the assessments collected during the post-treatment period will be flagged.

2.8.4.2 Vital signs

Vital sign assessments are performed in order to characterize basic body function. The following parameters were collected: height (cm), weight (kg), body temperature (°C), heart rate (beats per minute), systolic and diastolic blood pressure (mmHg).

Data handling

Vital signs collected on treatment will be summarized. Values measured outside of on treatment period will be flagged in the listings.

Data analysis

[figure not shown]
For analysis of vital signs the clinically notable vital sign criteria are provided in Table 2-7 below.

Table 2-7 Clinically notable changes in vital signs

Vital sign (unit)	Clinically notable criteria	
	above normal value	below normal value
Weight (kg)	increase > 10% from Baseline	decrease > 10% from Baseline
Systolic blood pressure (mmHg)	>=180 with increase from baseline of >=20	<=90 with decrease from baseline of >=20
Diastolic blood pressure (mmHg)	>=105 with increase from baseline of >=15	<=50 with decrease from baseline of >=15
Pulse rate (bpm)	>=100 with increase from baseline of >25%	<=50 with decrease from baseline of > 25%
Body temperature	>= 39.1	-

The number and percentage of subjects with notable vital sign values (high/low) will be presented.

A listing of notable vital values will be produced. In the listing, the assessments collected outside of on-treatment period will be flagged.

2.11 Interim analysis

Not applicable.

3 Sample size calculation

The operating characteristics of the design have been assessed via simulations (see Table 3-1 below). For each scenario, 1000 trials were simulated. A scenario was defined by assumption regarding the true PFS6 rate, an accrual rate of one patient per month with the final analysis taking place after the last patient completed 6 cycles of treatment or discontinued. A success was defined as follows:

Prob (PFS6 > 25%) > 80% and Prob (PFS6 > 40%) > 50% at the final analysis.

Table 3-1 Operating characteristics of study design

	True PFS6					
	0.16	0.25	0.35	0.4	0.45	0.5
Prob. of stopping at interim	0.870	0.506	0.165	0.082	0.035	0.014
Average sample size	21.589	27.016	31.799	32.922	33.547	33.822
Prob. of success (final)	0.000	0.003	0.227	0.488	0.746	0.917
Average study duration (months)	20.674	27.388	33.650	35.269	36.261	36.807

Assuming a true PFS6 rate of 50% and a uniform accrual of one patient per month, with 34 patients in total (~27 PFS events), there is about 92% chance to achieve success at the end of the study.

4 Change to protocol specified analyses

Interim analysis is planned in the CSP: an interim analysis for futility was planned to be carried out once 10 patients in the PPS have completed 6 cycles of treatment or discontinued earlier. No actual interim analysis was performed.

5 Appendix

5.1 Imputation rules

5.1.1 Study drug

The following rule should be used for the imputation of the dose end date for a given study treatment component:

Scenario 1: If the dose end date is completely missing and there is no EOT page and no death date, the patient is considered as on-going:

The patient should be treated as on-going and the cut-off date should be used as the dose end date.

Scenario 1 should not be applicable for final CSR. All patients should have EOT page complete before the Database lock for Final CSR

Scenario 2: If the dose end date is completely or partially missing and the EOT page is available:

Please note that date of assessment on EOT CRT might be very different from last date of dose.

Case 1: The dose end date is completely missing, and the EOT completion date is complete, then this latter date should be used.

Case 2: Only Year(yyyy) of the dose end date is available and yyyy < the year of EOT date:

Use Dec31yyyy

Case 3: Only Year(yyyy) of the dose end date is available and yyyy = the year of EOT date:

Use EOT date

Case 4: Both Year(yyyy) and Month (mm) are available for dose end date, and yyyy = the year of EOT date and mm < the month of EOT date:

Use last day of the Month (mm)

After imputation, compare the imputed date with start date of treatment, if the imputed date is < start date of treatment:

Use the treatment start date

Patients with missing start dates are to be considered missing for all study treatment component related calculations and no imputation will be made. If start date is missing then end-date should not be imputed.

5.1.2 AE, ConMeds and safety assessment date imputation

Table 5-1 Imputation of start dates (AE, CM) and assessments (LB, EG, VS)

Missing Element	Rule
day, month, and year	
 No imputation will be done for completely missing dates
day, month	
 If available year = year of study treatment start date then 
 If stop date contains a full date and stop date is earlier than study treatment start date then set start date = 01JanYYYY Else set start date = study treatment start date. If available year > year of study treatment start date then 01JanYYYY If available year < year of study treatment start date then 01JulYYYY

Missing Element	Rule
day	
• If available month and year = month and year of study treatment start date then
○ If stop date contains a full date and stop date is earlier than study treatment start date then set start date= 01MONYYYY.○ Else set start date = study treatment start date.• If available month and year > month and year of study treatment start date then 01MONYYYY• If available month and year < month year of study treatment start date then 15MONYYYY

Table 5-2 Imputation of end dates (AE, CM)

Missing Element	Rule (* = last treatment date plus 30 days not > (death date, cut-off date, withdrawal of consent date))
day, month, and year	
Completely missing end dates (incl. ongoing events) will be imputed by the end date of the on-treatment period*
day, month	
If partial end date contains year only, set end date = earliest of 31DecYYYY or end date of the on-treatment period *
day	
If partial end date contains month and year, set end date = earliest of last day of the month or end date of the on-treatment period*

Any AEs and ConMeds with partial/missing dates will be displayed as such in the data listings.

Any AEs and ConMeds which are continuing as per data cut-off will be shown as 'ongoing' rather than the end date provided.

The above imputations are only used for analyses of time to and duration of AEs and concomitant medications.

